8.3.6 Adverse Events of Special Interest

For this study, AESIs include only the following:

- Cytopenia (lymphopenia, leukopenia/neutropenia, thrombocytopenia, anemia), Grade ≥ 3 or with complications, e.g., neutropenia with fever or infection or thrombocytopenia with medically concerning bleeding.

An AESI (serious or nonserious reaction) is one of scientific and medical concern specific to the study intervention, for which ongoing monitoring and rapid communication by the Investigator to the Sponsor is required. Such events of interest may require further investigation or in-depth evaluations to better characterize and understand the association between the AE and M4076. Based on nonclinical data, the following AEs will be considered AESI (Table 11).

Table 11 Adverse Events of Special Interest

AE	Management
Cytopenias (lymphopenia, leuko/neutropenia, thrombocytopenia, anemia), Grade ≥ 3 or with complications, e.g. neutropenia with fever or infection or thrombocytopenia with medically concerning bleeding.	Repeat blood test within 72 hours of receiving the abnormal lab result. Continuous monitoring of AEs with clinical management as indicated, including study intervention interruption, dose modification or discontinuation (see Table 10).

AE = Adverse event.

The Investigator must complete the AESI Report Form and communicate with the Sponsor within 24 hours of occurrence of AESI. Serious AESI (based on SAE reporting criteria) should always be reported as SAE as outlined in Section [8.3.4](#).

8.4 Treatment of Overdose

For this study, any dose of M4076 greater than the specified dose for each study cohort will be considered an overdose.

The Sponsor does not recommend specific treatment for an overdose, other than symptomatic treatment of AEs as deemed necessary.

Even if not associated with an AE or an SAE, any overdose is recorded in the CRF and reported to global patient safety in an expedited manner. Overdoses are reported on an SAE and Overdose Report Form, following the procedure in [Appendix 4](#), the section on Reporting SAEs.

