4.1.1 Part 1A – M4076 Monotherapy Dose Escalation

Part 1A of the study will define the MTD and/or RDE of M4076 monotherapy in participants with advanced solid tumors for which no standard therapy is available.

The first dose escalation cohort of 3 participants will receive M4076 monotherapy at the starting dose of 100 mg administered orally once daily under fasting conditions (see Section 6.1 for fasting window information). For further dose escalation cohorts, an SMC will meet and review all available safety, PK and Pd data to provide recommendations on the DL for the next cohort. A Bayesian dose-toxicity model (Appendix 12) will assist the SMC in dose recommendations. For details of statistical considerations, see Section 9.

Potential DLs are: 100 mg (starting dose), 200 mg, 300 mg, 400 mg, 600 mg. A DL of 50 mg will be explored in case the starting dose of 100 mg is not tolerated. Depending on the observed toxicity profile and available PK and Pd, the SMC may decide on doses different to, or higher or lower from what is prespecified. The SMC may also recommend changing the dosing regimen to e.g. thrice weekly (daily dosing on Days 1, 3, and 5 of each week), twice weekly (daily dosing on Days 1 and 4 of each week), and/or schedules with holidays from study intervention (e.g., 3 days on/4 days off, 7 days on/14 days off, 14 days on/7 days off). More details on the SMC and dose escalation can be found in Section 6.6.1. The SMC operational details will be provided in an SMC Charter, which will be established prior to the start of recruitment. The details will include, but not limited to SMC membership, meeting frequencies, minimum requirements for data review, and responsibilities.

Dose escalation will proceed according to SMC recommendation until MTD and/or a safe RDE is determined and/or the SMC recommends ending dose escalation. The MTD and RDE are defined by the SMC. Target DLT probability for the MTD determination is 30%. In determining the RDE, the SMC will also consider PK, Pd and information on the safety and tolerability of the study intervention beyond the DLT period.

At least 6 participants are required to be treated at the MTD and/or RDE.

RDE cannot exceed MTD. If suggested RDE is below MTD, dose escalation will continue until MTD is reached (if applicable) or SMC decides ending dose escalation.

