At the discretion of the SMC, if the toxicity and tolerability profile of M4076 remains ambiguous at any DL, including the MTD or if additional PK/Pd data are felt necessary at any DL below the MTD, additional participants may be studied at that DL to better define the toxicity, tolerability, PK, and Pd. The study procedures for these additional participant(s)/cohort(s) will be the same as that specified for other study participants/cohorts.

This study part will also investigate the pharmacodynamics of M4076 as a secondary objective. Paired tumor biopsies (optional) and serial blood samples (mandatory) will be collected to evaluate markers of ATM inhibition.

If necessary, the Schedule of Activities will be adjusted, e.g. to ensure that PK and Pd samples are collected at the appropriate time points.

Once the MTD and/or RDE is determined in Part 1A, the RDE from Part 1A will be used for the food effect cohort in Part 1B.

Intraparticipant Dose Escalation: No intraparticipant dose escalation is allowed. However, upon declaration of safety and tolerability of the MTD or RDE by the SMC, participants who are still receiving ongoing study intervention at doses lower than the RDE may be switched to the RDE if participants have not experienced any treatment-emergent related AEs greater than Grade 1.

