6.6.2.1 Dose Interruptions and Modifications

Participants who experience an AE meeting DLT criteria during the DLT assessment period need to interrupt M4076 (Table 10). No dose modifications of M4076 should be made during the DLT assessment period for the dose escalation part of the study (Part 1A).

Participants who experience rash and systemic symptoms (e.g., fever, vomiting, diarrhea), or other signs of hypersensitivity should have M4076 discontinued immediately and are not to be rechallenged with any dose of M4076. Grade 2 and Grade 3 rash (without systemic symptoms) should be managed with treatment interruption and supportive medications, including topical or oral steroids.

Dose modifications outside the DLT period are allowed. Participants who experience a Grade 4 drug-related toxicity should discontinue treatment promptly. For a Grade 3 drug-related toxicity, M4076 treatment should be interrupted and may resume at a reduced dose provided the toxicity has resolved to Baseline value or Grade ≤ 1 within 2 weeks. At the first instance of a Grade 3 toxicity, study intervention will be held, and allowed to resume with a 25% dose reduction once said toxicity recovers to Grade ≤ 1 . Should a study participant develop a recurrent Grade 3 drug-related toxicity, study intervention will once again be held, and allowed to resume with a 50% dose reduction once said toxicity recovers to Grade ≤ 1 . Subsequent recurrences of Grade 3 toxicity will prompt discontinuation of study treatment, i.e., no more than 2 dose reductions will be permitted. Based on emerging data (i.e. toxicity, PK, Pd) and tablet strength availability, different dose reductions may be recommended as agreed between Sponsor and investigator, such as alternative dose reduction steps or different dosing regimen. Recommended dose reductions for each potential DL are provided in [Table 10](#).

Once the dose of M4076 has been reduced in an individual participant, it must not be escalated back to the original dose level. If more than 2 dose reductions of $> 50\%$ dose decrease are indicated, the participant will be permanently discontinued from study intervention. Consultation between Investigator and Sponsor about dose reduction is encouraged.

Table 10 M4076 Recommended Dose Modifications for Grade 3 Hematologic and Nonhematologic ADRs

Potential DLs – Starting doses	Grade 3 Hematologic and Nonhematologic ADRs		
	1 st occurrence DR of 25%	2 nd occurrence DR of 50%	3rd occurrence

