### Definition of actual dose

Unless otherwise specified, analyses of safety, efficacy and PK parameters will be conducted by actual dose. In this open label, unblinded study, actual dose is determined by considering study drug compliance during the DLT evaluation period (first 21 days from first dose of M4076) and whether the subject experienced a DLT (as per SMC determination). If a different regimen is tested, all subjects remain in the regimen to which they were assigned (i.e. subjects cannot be assigned to a different pre-specified dose level with a different dosing scheme).

In this context, compliance is defined as the cumulative actual dose taken by the subject divided by the cumulative cohort-level planned dose the subject was expected to receive. The planned dose level will be taken from the electronic case report form (eCRF) “Cohort”. The following table will be used to determine actual dose level:

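### Protocol Section 8.4 measures overdose against the cohort dose, so its expedited report does not track participants whose own dose has been reduced or switched to the RDE

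*Protocol*

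**What the plan says.** **Overdose (Protocol 8.4).** This is the only definition of overdose in the documents: "any dose of M4076 greater than the specified dose for each study cohort will be considered an overdose". The consequence is that "any overdose is recorded in the CRF and reported to global patient safety in an expedited manner". This applies even when no adverse event occurs.

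**Doses below the cohort dose (Protocol 6.6.2.1 and Table 10).** At a first Grade 3 drug-related toxicity, "study intervention will be held, and allowed to resume with a 25% dose reduction". At a recurrence, "study intervention will once again be held, and allowed to resume with a 50% dose reduction". The reduction is one-way: "Once the dose of M4076 has been reduced in an individual participant, it must not be escalated back to the original dose level". Table 10 turns these steps into doses for each dose level.

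**Doses above the cohort dose (Protocol 4.1.1).** Escalation within a participant is otherwise ruled out. Once the SMC has declared the MTD or RDE safe and tolerable, however, "participants who are still receiving ongoing study intervention at doses lower than the RDE may be switched to the RDE", provided they have had no related treatment-emergent event above Grade 1.

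**Dose levels (Protocol 4.1.1).** "Potential DLs are: 100 mg (starting dose), 200 mg, 300 mg, 400 mg, 600 mg".

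**SAP Section 9, definition of actual dose.** Planned dose comes from the eCRF cohort entry. Actual dose is settled by compliance in the first 21 days and by DLT status. Neither is updated for a later reduction or switch.

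**The concern.** Section 8.4 takes the cohort's dose as its yardstick, but the protocol creates two groups whose correct dose is not the cohort's dose.

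- **Reduced participants.** Section 6.6.2.1 forbids a return to the original dose. If such a participant takes that dose by mistake, the amount equals the cohort dose and does not exceed it, so the event is not an overdose under 8.4. These participants have already had a Grade 3 drug-related toxicity.
- **Switched participants.** Someone moved to the RDE under 4.1.1 takes more than the original cohort's dose on every day of correct RDE dosing. Read literally, each of those doses is an overdose that needs an expedited report.

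At stake is whether expedited overdose reporting in a first-in-human study identifies the right events. The error is a plausible one: the only tablet strength is 50 mg (Protocol 6.1, Table 8), so a reduction changes the tablet count and not the product, and Protocol 6.4 provides for self-administration at home.

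**Working it through.** The plan gives no figure to reproduce. The check applies the 8.4 rule to each dose state that the protocol itself creates.

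**Inputs.** Reduction steps from Protocol Table 10; dose levels 100, 200, 300, 400 and 600 mg from Protocol 4.1.1; the overdose rule from Protocol 8.4.

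**Rule as written.** Overdose if dose taken > cohort dose.

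**Step 1: a reduced participant takes the former cohort dose.** The dose taken equals the cohort dose, so the test is cohort dose > cohort dose, which is never true. Excess over the assigned dose = cohort dose / reduced dose.

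| Cohort (mg) | Reduced to (mg) | Taken / assigned | Overdose under 8.4? |
|---|---|---|---|
| 100 | 50 | 100/50 = 2.00 | No |
| 200 | 150 | 200/150 = 1.33 | No |
| 200 | 100 | 200/100 = 2.00 | No |
| 300 | 200 | 300/200 = 1.50 | No |
| 300 | 150 | 300/150 = 2.00 | No |
| 400 | 300 | 400/300 = 1.33 | No |
| 400 | 200 | 400/200 = 2.00 | No |
| 600 | 450 | 600/450 = 1.33 | No |
| 600 | 300 | 600/300 = 2.00 | No |

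Result: 0 of 9 states are flagged. The ratio is 2.00 in five states, 1.50 in one and 1.33 in three.

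**Step 2: a switched participant correctly takes the RDE.** The test is RDE > original cohort dose, with ratio RDE / cohort dose. The RDE is not known in advance, so every pair of a lower cohort with a higher listed level is shown.

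| RDE (mg) | Lower cohorts (mg) and ratio | Overdose under 8.4? |
|---|---|---|
| 200 | 100: 2.00 | Yes |
| 300 | 100: 3.00; 200: 1.50 | Yes, both |
| 400 | 100: 4.00; 200: 2.00; 300: 1.33 | Yes, all three |
| 600 | 100: 6.00; 200: 3.00; 300: 2.00; 400: 1.50 | Yes, all four |

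Result: 1 + 2 + 3 + 4 = 10 of 10 pairs are flagged.

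**Step 3: limit of step 2.** A switched participant may later be reduced under Table 10. With cohort 200 mg and RDE 300 mg, the first reduction is to 200 mg, and 200 > 200 is false, so those doses are not flagged. The statement in step 2 therefore covers doses taken at the RDE, not all doses after a switch.

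**Step 4: sensitivity to the reference dose.** If the test is run against the dose currently assigned to the participant, all 9 states in step 1 are flagged and none of the 10 pairs in step 2 is. Both classifications reverse completely, so the missing statement of the reference dose decides the result.

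**The case against.** The strongest reply has four parts.

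1. **The wrong dose is not lost.** A reader might infer that nothing is recorded when a reduced participant takes the former dose. The documents do not support that. Protocol 6.4 puts any departure from the prescribed regimen in the CRF, backed by questioning and tablet counts. SAP 10.2.1 counts receipt of an incorrect dose as an important protocol deviation, to be tabulated and listed. SAP Section 13 lists all administrations. Adverse events, SAEs and Grade 3 or higher cytopenias remain reportable by their own routes (Protocol 8.3.1, 8.3.6 and Appendix 4). This stands. It narrows the loss to the overdose label and the expedited report, which 8.4 wants even without an adverse event.

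2. **No effect on decisions or results is shown.** A reader might also infer that the safety record seen by the SMC and in the CSR is distorted. The visible SAP safety sections contain no overdose table, listing or endpoint, and the SMC analysis plan (SAP Appendix 18.2) is not in the available text. Dose modifications are barred during the Part 1A DLT period, and the switch becomes available only after the SMC has declared the MTD or RDE safe and tolerable. This stands: distortion of SMC or CSR output cannot be claimed.

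3. **The switch is optional and conditional.** It needs participants still on treatment below the RDE, with no related event above Grade 1, in a study where average participation is put at about 15 weeks. The numbers may be small. This stands as a limit on frequency, not on the logic.

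4. **A site could read the specified dose as following the participant.** That may be the intention, and the CRF completion conventions or overdose form, which are not supplied, may say so. But neither the protocol text nor the SAP says it, and the wording of 8.4 names the cohort. This part does not remove the point.

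**Conclusion.** The inconsistency is real. Applied as written, Section 8.4 classifies both groups against a dose that is no longer theirs. It flags 0 of the 9 Table 10 reduction states when the former cohort dose is taken (1.33 to 2.00 times the assigned dose), and it flags correct dosing in all 10 possible switches to the RDE among the listed levels.

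The scope is limited to overdose classification and expedited reporting. It would go too far to say that every dose after a switch is an overdose, because a later reduction can bring the dose to or below the original cohort dose. The DLT model, sample size and efficacy analyses are not shown to be affected.

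The conclusion assumes that a participant stays in the original cohort after a reduction or switch, since no passage moves them and the SAP keeps the eCRF cohort entry. It also uses the Table 10 steps and the listed levels. Protocol 4.1.1 and 6.6.2.1 allow other levels and other reduction steps, which would change the ratios but not the logic.

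**What to change.** Reconcile Protocol 8.4 with 4.1.1 and with 6.6.2.1 and Table 10, so that 8.4 states expressly which dose is the reference for overdose reporting in a participant whose dose has been reduced and in one who has been switched to the RDE. Check the CRF instruction and the overdose report form against that statement and align them if needed. No dose level, reduction step or switching condition needs to change.

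The cost is one sentence in the protocol and, if the operational documents do not already cover it, a matching line there. No analysis in the SAP has to be altered.

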8.5 Pharmacokinetics

Sampling times for the determination of M4076 can be found in [Table 3](#) for Part 1A and [Table 4](#) for Part 1B. The PK sampling schedule may be modified upon agreement of the clinical pharmacologist, investigators, and SMC to optimize the definition of the pharmacokinetic profiles but will not increase the number of PK draws.

The following PK parameters will be calculated, when appropriate (see [Table 12](#)). A non-compartmental analysis (NCA) will be performed to estimate these PK parameters for M4076.

Table 12 Assessment of Blood Pharmacokinetic Parameters

Symbol	Definition
AUC _{0-t_{last}}	The area under the concentration-time curve (AUC) from time zero (= dosing time) to the last sampling time (t_{last}) at which the concentration is at or above the lower limit of quantification. Calculated using the mixed log-linear trapezoidal rule (linear up, log down).
AUC _{0-t_{last}} /Dose	The Dose normalized AUC from time zero to the last sampling time (t_{last}) at which the concentration is at or above the lower limit of quantification. Normalized using the actual dose, using the formula $AUC_{0-t_{last}}/Dose$.

Symbol	Definition
AUC _τ	The AUC over the dosing interval from $T_1 = 0$ h to $T_2 = \tau$ h. Calculated using the mixed log-linear trapezoidal rule (linear up, log down). For single dose, AUC _τ is calculated as a partial area with the defined time range. In multiple dose profiles AUC _τ is calculated at steady state from one pre-dose time point to the dosing interval time. In cases where the actual observation time is not equal to the scheduled observation time AUC _τ will be calculated based on the estimated concentration at τ hours, and not the concentration at the actual observation time.
AUC _τ /Dose	The dose normalized AUC over the interval from $T_1 = 0$ h to $T_2 = \tau$ h. Normalized using actual dose, using the formula AUC _τ /Dose.
AUC ₀₋₇₂	The AUC from time zero (= dosing time) to 72 hours post-dose. Calculated using the mixed log-linear trapezoidal rule (linear up, log down). In cases where the actual observation time is not equal to the scheduled observation time (72 hours), AUC ₀₋₇₂ will be calculated based on the estimated concentration at 72 hours, and not the concentration at the actual observation time.
AUC ₀₋₇₂ /Dose	The dose normalized AUC from time zero (= dosing time) to 72 hours post-dose. Normalized using actual dose, using the formula AUC ₀₋₇₂ /Dose.
AUC _{0-∞}	The AUC from time zero (dosing time) extrapolated to infinity, based on the predicted value for the concentration at t_{last} , as estimated using the linear regression from λ_z determination. $AUC_{0-∞} = AUC_{0-t_{last}} + C_{last\ pred} / \lambda_z$
AUC _{0-∞} /Dose	The dose normalized AUC from time zero extrapolated to infinity. Normalized using actual dose, using the formula AUC _{0-∞} /Dose.
CL/F	The apparent total body clearance of study intervention following extravascular administration. $CL/F = Dose_{p.o.} / AUC_{0-∞}$.
C _{max}	Maximum observed concentration
C _{max} /Dose	The dose normalized maximum concentration. Normalized using the actual dose, and the formula C _{max} /Dose.
C _{trough}	The concentration observed immediately before next dosing
LI	The linearity index after repeated administration calculated as $LI = (AUC_{\tau} \text{ after multiple dose}) / (AUC_{0-∞} \text{ after single dose})$
R _{acc} (AUC _τ)	The accumulation ratio after repeated administration calculated as $R_{acc}(AUC_{\tau}) = (AUC_{\tau} \text{ after multiple dose}) / (AUC_{\tau} \text{ after single dose})$
R _{acc} (C _{max})	The accumulation factor to assess the increase in maximum concentration until steady state is reached. $R_{acc}(C_{max}) = (C_{max} \text{ after multiple dose}) / (C_{max} \text{ after single dose})$
t _{1/2}	Apparent terminal half-life. $t_{1/2} = \ln(2) / \lambda_z$
t _{last}	The last sampling time at which the concentration is at or above the lower limit of quantification
t _{max}	The time to reach the maximum observed concentration collected during a dosing interval (unless otherwise defined, take the 1 st occurrence in case of multiple/identical C _{max} values)
V _z /F	The apparent volume of distribution during the terminal phase following extravascular administration. $V_z/F = Dose / (AUC_{0-∞} * \lambda_z)$ following single dose. $V_z/F = Dose / (AUC_{\tau} * \lambda_z)$ following multiple dose.

- Whole blood samples (of approximately 2 mL) and urine samples (Part 1B only) will be collected for measurement of plasma and urine concentrations of M4076. Collection times are specified in the Schedule of Activities (Table 3 for Part 1A and Table 4 for Part 1B). The actual date and time (24-hour clock) of each sample will be recorded to calculate actual time

elapsed since the prior dose administration. The sampling timing may be altered during the study based on newly available data (e.g., to obtain data closer to the time of peak plasma concentrations) to ensure appropriate monitoring. In addition, actual date and time of start and end of the urine collection fraction and the volume of each urine collection fraction will be recorded in the CRF.

- The quantification of M4076 concentrations in plasma and urine will be performed using validated bioanalytical methods and will be reported in a separate bioanalytical report. Concentrations will be used to evaluate the PK of M4076.
- Remaining samples collected for the analysis of M4076 plasma and urine concentrations may be used to evaluate safety or efficacy aspects related to concerns arising during or after the study, which will be reported outside of the clinical study report (CSR).
- The following pharmacokinetic parameters will be estimated from urine concentration of M4076 in Part 1B ([Table 13](#)), where possible:

Table 13 Assessment of Urine Pharmacokinetic Parameters

[figure not shown]
Symbol	Definition
Ae_{t1-t2}	Total amount excreted between times t_1 (= start) and t_2 (= end) of the current collection interval. Calculated by interval $Ae_{t1-t2} = \text{Conc} * Vu_{(t1-t2)}$ and cumulative.
$fe_{t1-t2} \%$	Fraction of administered drug that is excreted unchanged in urine between times t_1 (= start) and t_2 (= end) of the current collection interval. Calculated by interval $fe_{t1-t2} = Ae_{t1-t2}/\text{Dose}$ and cumulative.
CL_R	The renal clearance of study intervention. $CL_R = Ae_{0-t}/AUC_{0-t}$.

Additional parameters may be calculated if appropriate.

[figure not shown]
Methodology for the calculation of pharmacokinetic parameters will be detailed in the Integrated Analysis Plan (iAP).

- Details on processes for collection and handling of these samples are in the Laboratory Manual. Retention time and possible analyses of samples after the end of study are specified in the respective ICF.

CCI

CCI

CCI

